13.1.3. Primary Efficacy Analysis

The primary efficacy endpoint will be the time to first occurrence of one of the following post-randomization:

- Death (all-cause)
- Liver transplant
- MELD score ≥ 15
- Hospitalization (as defined by a stay of 24 hours or greater) for new onset or recurrence of:
 - Variceal bleed
 - Encephalopathy (as defined by a West Haven score of ≥ 2)
 - Spontaneous bacterial peritonitis (confirmed by diagnostic paracentesis)
- Uncontrolled ascites (diuretic resistant ascites requiring therapeutic paracentesis at a frequency of at least twice in a month).
- Hepatocellular carcinoma confirmed by 2 complimentary imaging modalities.

The primary efficacy analysis will compare randomized OCA to randomized placebo with respect to the primary efficacy endpoint using the ITT population. Only adjudicated events will be included in analyses. The 2 treatment groups will be compared using the log rank test stratified by the randomization stratification factor. Kaplan-Meier (KM) estimates of the distribution of the time-to-event will be tabulated and graphed by treatment group. The tabulation will include the KM estimate of the medians and corresponding 95% confidence intervals (CIs), if the medians can be estimated. The number and percent of subjects censored and with events will be presented. The hazard ratio and 95% CI will be determined based on a Cox regression model stratified by randomization strata to estimate the magnitude of the effect.

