13.1.5. Additional Secondary Efficacy Analyses

The following time to event secondary efficacy analyses will compare randomized OCA versus randomized placebo using the ITT population:

- Time to each component of the primary efficacy endpoint (except MELD score ≥ 15 which is captured above)
- Time to development of varix/varices
- Time to liver-related death
- Time to liver-related death or liver transplant
- Time to liver-related death, liver transplant, or MELD score ≥ 15

The same analysis methodology as used for the primary efficacy analysis will be used for these secondary efficacy analyses. Similar endpoints, where available, will be analyzed to compare OCA to historical controls as described below in [Section 13.1.8](#).

Analyses of changes in liver biochemistry (GGT, ALT, AST, conjugated bilirubin, albumin, and INR) will be summarized and analyzed using the same methodology as specified in [Section 13.1.4](#) for the key secondary analyses of change in ALP and total bilirubin.

Analyses of changes in MELD score, Child-Pugh score, Mayo Risk Score (MRS), IgM, CRP, TNF- α , FGF-19, CK-18, C4, and ELF score will be summarized and analyzed using the Wilcoxon Rank Sum Test to compare treatment groups. The median differences and 95% CI of the median differences between treatment groups will be constructed using Hodges-Lehmann estimate. If the median differences between treatments are not symmetrical around the median, the Sign Test may be used.

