Propensity scores will be estimated using the available covariates that predict receiving the treatment. Only covariates and not outcome variables will be included in the propensity score estimation. Therefore, there is no chance of biasing results in favor of one treatment.

The covariates and factors collected in the historical databases will be specified in the SAP.

Propensity scores will be estimated first through a logistic regression model with treatment group as the dependent variable and the above covariates/factors as independent variables. Then the stratum boundaries are determined based on the propensity score values for both groups (OCA population and control [historical and randomized placebo]) combined or in the OCA population or historical control group alone. Based on recommendations in the literature, quintiles of the estimated propensity score from the combined group will be used to determine the stratum boundary cut-offs for the different strata.

Outcome events collected in the historical database are: death (liver-related and all-cause), liver transplant, hepatocellular carcinoma, and other. Other is defined as cirrhosis or decompensation such as ascites, variceal bleed, and encephalopathy.

The propensity score quintile will be then be used as the stratification factor in the stratified log rank test to compare randomized OCA-treated subjects in the ITT population and historical controls (Overall Historical Control Population: both the UK-PBC Group and Global PBC Study Group databases) on the following outcomes:

- Time to death (all-cause)
- Time to liver-related death
- Time to liver transplant
- Time to liver transplant or death (all-cause)

- Time to liver transplant or liver-related death
- Time to hepatocellular carcinoma

KM estimates of the distribution of the time-to-event will be tabulated and graphed by treatment group. The tabulation will include the KM estimate of the medians and corresponding 95% CIs if the medians can be estimated. The number and percent of subjects censored and with events will be presented. The hazard ratio and 95% CI will be determined based on a Cox regression model stratified by randomization strata to estimate the magnitude of the effect.

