13.1.10.1. Time to Event Endpoints

For the time to event analyses, subjects who do not experience an event will be censored at the time of their last contact. Subjects with no data after randomization will be considered to have an event on Day 1 (first day of investigational product dosing).

For analyses of the percentage of subjects with an event, subjects with no data after randomization will be considered to have an event.

All time to event endpoints include only adjudicated events. Sensitivity analyses may consider all events regardless of adjudication. Events with discrepant adjudication will be analyzed using both results.

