7.4.1. Safety Criteria for Adjustment or Stopping Doses

Investigational product may be temporarily decreased (ie, from 10 mg to 5 mg daily, or by alternate day dosing) or temporarily or permanently stopped based on tolerability concerns. The dose of investigational product should be resumed to the maintenance dose in a blinded manner (5 mg or 10 mg) once the issues relating to the lack of tolerability are resolved.

Subjects that discontinue investigational product are expected to continue in the study (and follow the regular visit schedule) until the end of the study, and the study will only terminate at the time when the needed number of adjudicated events has accrued. If a subject reaches an event, he or she should continue the regular visit schedule and continue taking investigational product as long as the Investigator assesses it as safe. In general, subjects should be strongly encouraged to both stay on investigational product and remain in the study until study termination.

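### Kaplan-Meier curves for the non-fatal components, varices and liver-related death treat earlier deaths as censoring and so overstate absolute incidence

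*Protocol*

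**What the plan says.** Section 13.1.3 sets the primary method: a stratified log-rank test, a stratified Cox model and, as the display, "Kaplan-Meier (KM) estimates of the distribution of the time-to-event will be tabulated and graphed by treatment group".

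Section 13.1.5 lists further endpoints, among them "Time to each component of the primary efficacy endpoint (except MELD score" (that one component sits with the key secondaries in Section 13.1.4), time to varices, and "Time to liver-related death". It then says: "The same analysis methodology as used for the primary efficacy analysis will be used for these secondary efficacy analyses". Section 13.1.8 compares OCA with historical controls on transplant, liver-related death and hepatocellular carcinoma, among others, and again "KM estimates of the distribution of the time-to-event will be tabulated and graphed by treatment group".

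Section 13.1.10.1 holds the only censoring rule: "subjects who do not experience an event will be censored at the time of their last contact". Competing risks and cumulative incidence are not mentioned.

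Section 7.4.1 bears on transplant: "If a subject reaches an event, he or she should continue the regular visit schedule".

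These section texts are from Amendment 1. The copy of Amendment 1.1 at hand ends before Section 13, but its synopsis repeats both the Kaplan-Meier method and the sentence that carries it over.

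**The concern.** Death removes any chance of a later transplant, hepatocellular carcinoma, decompensation event or varix, and a non-liver death removes any chance of liver-related death. Last contact for such a subject is in effect the death, so the rule censors there. Kaplan-Meier then treats the dead subject as someone who could still have had the event at the rate of those alive. Its complement estimates a risk in a setting where nobody dies of anything else, not the proportion of patients who have the event.

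At stake is the absolute risk by arm that a reader takes from the component curves. The size of the error depends on the competing death rate. If OCA lowers that rate, the error is larger on placebo and does not cancel in the difference between arms.

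**Working it through.** **Reproducing the plan's own figure.** Inputs from Section 13.1.2: hazard ratio 0.60, two-sided 5%, 80% power, 1:1. Schoenfeld events = 4 × (1.960 + 0.842)² / (ln 0.60)² = 4 × 7.85 / 0.261 ≈ 120.3, rounded up to 121. This matches the protocol; power at 121 events is 80.2%.

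**Hazards implied by the plan.** Exponential curves with placebo event-free probability 0.5 at 8 years give a composite hazard of ln 2 / 8 = 0.0866 per year on placebo and 0.60 × 0.0866 = 0.0520 per year on OCA.

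**Assumptions.** No component or competing-death rate is given, so both are set as shares of the composite hazard: component 20%, competing death 10%, 20%, 30% or 50%, with the hazard ratio of 0.60 applied to both. The shares set a scale and are not a partition of the composite, because Section 13.1.5 counts each component even after another has occurred.

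**Formulas**, with component hazard a, competing hazard b, at 8 years:

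- One minus Kaplan-Meier with deaths censored: 1 − exp(−8a)
- Cumulative incidence: a/(a+b) × [1 − exp(−8(a+b))]

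**Kaplan-Meier.** Placebo: 1 − exp(−8 × 0.2 × 0.0866) = 12.9%. OCA: 1 − exp(−8 × 0.2 × 0.0520) = 8.0%. Difference: 5.0 points.

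**Cumulative incidence.** For example, placebo with a 50% competing share: 0.2/0.7 × [1 − exp(−8 × 0.7 × 0.0866)] = 11.0%.

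| Competing share | Placebo incidence | KM excess, placebo | OCA incidence | KM excess, OCA | Difference between arms | KM difference too large by |
|---|---|---|---|---|---|---|
| 10% | 12.5% | 0.4 points (3%) | 7.8% | 0.2 points (2%) | 4.7 points | 6% |
| 20% | 12.1% | 0.8 points (7%) | 7.7% | 0.3 points (4%) | 4.4 points | 12% |
| 30% | 11.7% | 1.2 points (10%) | 7.5% | 0.5 points (6%) | 4.2 points | 18% |
| 50% | 11.0% | 2.0 points (18%) | 7.2% | 0.8 points (11%) | 3.8 points | 32% |

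The last column is the Kaplan-Meier difference (4.96 points unrounded) divided by the cumulative-incidence difference, minus one.

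**Transplant as an intermediate event.** By the text, a transplanted subject stays on visits and in the risk set until last contact. Take placebo shares of 20% for the component, 30% for death and 20% for transplant, with no component event after transplant and an assumed post-transplant death hazard of 0.03 per year. Numerical integration over 8 years gives:

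- cumulative incidence: 11.0%
- Kaplan-Meier under the protocol's rule (deaths censored, transplanted subjects kept at risk): 12.1%
- Kaplan-Meier if transplants were censored as well: 12.9%

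The excess is 1.1 points under the protocol's rule and would be 2.0 points if transplants were censored.

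**The case against.** The strongest reply is that little depends on these curves. The log-rank test and Cox model remain valid as cause-specific comparisons. The endpoints in Section 13.1.5 lie outside the hierarchy in Section 13.1.11 and are descriptive. The plan also reports the number and percentage of subjects with events, which are crude proportions that censoring deaths does not inflate. A SAP could add cumulative-incidence displays. All of this stands and limits the weight of the point. It does not remove it, because the protocol names the estimator rather than leaving the choice open.

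A reader might infer more than the text supports:

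- **That transplants are censored too.** Sections 7.4.1 and 13.1.10.1 together keep transplanted subjects under follow-up and censor at last contact. The open matter is that no rule for transplant is stated.
- **That the bias could reach 38%.** Hazards of 0.03 for the event and 0.09 for competing death give 21.3% against 15.4%. Their sum of 0.12 per year implies that 1 − exp(−0.96) = 61.7% have the component or die within 8 years. Where the event is itself part of the composite, as death is, this cannot exceed the 50% planned for placebo.
- **That reported medians mislead.** Section 13.1.3 gives medians only where they can be estimated, and at these incidences none would be reached.
- **That cost-effectiveness results are distorted.** Section 13.1.7 defers to a separate economic plan and does not say that these curves feed it.

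**Conclusion.** The point holds as one of absolute-risk display. It covers transplant, hepatocellular carcinoma, hospitalised decompensation, uncontrolled ascites, varices and liver-related death in Section 13.1.5, those of them repeated in Section 13.1.8, and the Kaplan-Meier display of time to MELD ≥15 in Section 13.1.4.

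The direction is certain whenever some subjects die first without the event. The size is not known from the protocol. Under constant hazards and the assumed shares it is modest: 0.4 to 2.0 points on placebo and 0.2 to 0.8 on OCA. The overstatement of the difference between arms further assumes that the planned hazard ratio applies to the component and to competing death alike.

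No confirmatory conclusion changes. All-cause death, transplant or all-cause death, and the primary composite have no competing death and are correctly shown by Kaplan-Meier. This is a free improvement, not a flaw in the trial's main inference.

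**What to change.** In Sections 13.1.5 and 13.1.8, and for the display of time to MELD ≥15 in Section 13.1.4:

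- Replace Kaplan-Meier with the Aalen-Johansen cumulative incidence by arm, with death as the competing event. For liver-related death, and for composites that contain it, the competing event is non-liver death.
- Keep the stratified log-rank test and stratified Cox hazard ratio, labelled as cause-specific.
- State how transplant is handled for hepatocellular carcinoma and liver-related death: as a competing event, or with the subject kept at risk until last contact as the present text implies.
- Keep Kaplan-Meier for the primary composite, all-cause death, and transplant or all-cause death.

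The cost is a wording change in the protocol or SAP and the matching table and figure shells. No new data, subjects or follow-up are needed, and neither type I error nor power is affected.

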13.1.2. Determination of Sample Size

The following assumptions were used in sample size calculations:

- Exponential survival curves, placebo survival estimate of 0.5 at 8 years with a hazard ratio of 0.60, and total study duration of 8 years, allowing for 2 years accrual and 6 years of follow up.
- 5% of the subjects will have never been treated with UDCA; 95% of the subjects will have been on UDCA for at least 1 year.
- Subjects will be randomized in a 1:1 ratio to placebo or OCA.
- The 2 groups will be compared using a 2-sided log rank test at the 5% level of significance.

Based on the randomization ratio, significance level, and assumed hazard ratio, a total of 121 events (both groups combined) will provide 80% power to demonstrate a statistically significant difference between OCA and placebo on time to liver-related outcomes, including all-cause mortality.

In addition, based on the remaining assumptions stated above, it is estimated that approximately 350 subjects will be enrolled to attain 121 events.

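### The optional Sign Test for ten exploratory markers does not fit two independent arms, and its symmetry trigger belongs to a different test

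*Protocol*

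**What the plan says.** Section 13.1.5 (Additional Secondary Efficacy Analyses) takes the changes in ten measures: MELD score, Child-Pugh score, Mayo Risk Score, IgM, CRP, TNF-α, FGF-19, CK-18, C4 and ELF score. They are to be "analyzed using the Wilcoxon Rank Sum Test to compare treatment groups", with a Hodges-Lehmann estimate and 95% interval for the difference. No stratification factor or baseline covariate is named. The fall-back follows: "If the median differences between treatments are not symmetrical around the median, the Sign Test may be used".

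The neighbouring analyses do use the randomization strata: the log-rank test and Cox model in 13.1.3, the ANCOVA for ALP and total bilirubin in 13.1.4, and the Cochran-Mantel-Haenszel test in 13.1.6.1. The ANCOVA also includes baseline, and 13.1.5 applies it to GGT, ALT, AST, conjugated bilirubin, albumin and INR.

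Section 13.1.11 limits the testing hierarchy to the primary and four key secondary endpoints, and treats tests on all other efficacy endpoints as descriptive and exploratory.

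The wording quoted here is that of Amendment 1 and is the same in the original protocol. The Amendment 1.1 text at hand stops at Section 9.7.9, so its Section 13 could not be checked.

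**The concern.** The secondary objective in Section 6.2 is the effect of OCA compared with placebo on markers of inflammation and fibrosis. The Sign Test counts positive and negative values in one sample, or in the differences of matched pairs. Nothing in the protocol matches an OCA subject to a placebo subject. The condition that triggers the fall-back, symmetry around the median, is an assumption of the Wilcoxon signed-rank test for one sample or paired data. The rank-sum test does not need it. Trigger and fall-back both look borrowed from another design. An analyst who followed the sentence would report either a result that does not compare the arms, or a comparison weaker than the one it replaced.

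**Working it through.** **The plan's own figure.** The ten-marker analysis states no figure; the only design figure is the event count in 13.1.2. Inputs: "The 2 groups will be compared using a 2-sided log rank test at the 5% level of significance"; hazard ratio 0.60; "Subjects will be randomized in a 1:1 ratio to placebo or OCA". By Schoenfeld's formula, events = 4 × (1.960 + 0.842)² / (ln 0.60)² = 4 × 7.851 / 0.261 = 120.3, rounded up to 121. That reproduces "a total of 121 events (both groups combined) will provide 80% power"; the power at 121 events is 80.2%. Nothing below enters this figure. The planned 350 subjects at 1:1 give 350 / 2 = 175 per arm, which the simulations use.

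**Use within an arm.** Count the subjects in one arm whose change is positive and refer the count to Binomial(n, 0.5). The null hypothesis is a median change of zero in that arm; the other arm does not enter. To show the consequence, skewed (shifted lognormal) changes were simulated identically in both arms, so there was no treatment effect, with a common drift added (2000 runs per setting; distribution and drift assumed):

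| Common drift | Sign Test significant, OCA arm | Arms give different verdicts | Rank-sum test significant |
|---|---|---|---|
| 0 | 4.8% | 9.9% | 5.1% |
| 0.1 | 18.6% | 31.0% | 5.5% |
| 0.2 | 67.3% | 44.1% | 5.5% |
| 0.3 | 96.9% | 6.7% | 5.0% |

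The within-arm test responds to drift that both arms share. The rank-sum test does not.

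**Use on arbitrary pairs.** Pair OCA and placebo subjects at random and apply the Sign Test to the differences. In a null run (correlation 0.5, stratum effect 0.5 SD) this rejected in 4.5% of runs, so the level holds. Its power is in the last column of the second table. The result also depends on which random pairing was drawn.

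**The trigger.** If OCA changes are placebo changes shifted by δ, the between-arm pairwise differences are symmetric around δ however skewed the changes are. Asymmetry in them would therefore mean that the two arms differ in shape. That affects how the Hodges-Lehmann shift is read; it is no reason to move to a one-sample test. The first table shows the rank-sum test keeping its level on skewed data.

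**Baseline and strata.** With baseline and follow-up of unit variance and correlation r, the variance of change is 2(1 − r) and the linear ANCOVA residual variance is 1 − r². The saving is 1 − (1 − r²) / [2(1 − r)] = (1 − r) / 2, which is 25%, 15% and 10% at r = 0.5, 0.7 and 0.8. These are linear-model figures. For ranks, power was simulated with a shift of 0.3 SD and 1000 runs per setting. Two equal strata stood in for the four randomization cells, and the rank ANCOVA adjusted ranked change for ranked baseline and stratum:

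| Correlation | Stratum effect (SD) | Rank-sum | Stratified rank-sum (van Elteren) | Rank ANCOVA | Sign Test, random pairs |
|---|---|---|---|---|---|
| 0.3 | 0 | 65.6% | 65.1% | 80.5% | 47.9% |
| 0.5 | 0 | 78.4% | 77.9% | 87.1% | 60.7% |
| 0.7 | 0 | 93.8% | 93.5% | 96.8% | 80.5% |
| 0.3 | 0.5 | 62.1% | 64.0% | 79.9% | 44.1% |
| 0.5 | 0.5 | 77.3% | 78.1% | 88.7% | 56.8% |
| 0.7 | 0.5 | 93.2% | 94.5% | 97.5% | 79.2% |

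Stratification alone moves power by less than 2 points. Baseline gives most of the gain, and that gain shrinks as the correlation rises. In the null run the rank-sum, van Elteren and rank ANCOVA tests rejected in 5.2%, 6.0% and 6.1% of runs; the simulation standard error there is √(0.05 × 0.95 / 1000) = 0.7 points.

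**The case against.** The strongest reply is that the planned analysis is the rank-sum test on change, which is a valid randomized comparison, and that the Sign Test is only permitted, not required. Section 13 leaves analysis details to the SAP, which is not at hand, and strata or covariates for exploratory rank tests are commonly settled there. Giving ANCOVA to routine biochemistry and a rank method to scores and biomarkers is a defensible split. All of this stands, and it is why the absence of strata and baseline is treated here only as room for improvement.

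Three narrower replies also stand. Analysing change already subtracts baseline, so what is missing is covariate adjustment. The Sign Test is not confined to within-arm use, because random pairing keeps its level, at a cost in power. And the Hodges-Lehmann interval is conventionally obtained by inverting the rank-sum test, so the existing test and estimate belong together; an unadjusted interval beside a rank ANCOVA p-value could disagree with it.

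None of this rescues the sentence. Making a wrong fall-back optional does not make it right, and a SAP that follows the protocol would inherit it.

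**Conclusion.** The Sign Test sentence is wrong as written: the test is for one sample or pairs, and the trigger is not a condition of the test it is meant to replace. That follows from the design and rests on no assumed number. The sizes do rest on assumptions. The shift, correlations, skewness, drift and stratum effect are all assumed, since the protocol gives none of them.

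A reader might go further and infer that the main comparison of the ten markers is invalid because it is unstratified and unadjusted, or that the trial's conclusions are at risk. The documents do not support either. The rank-sum test kept its level, the ten tests lie outside the hierarchy in 13.1.11, and error control for the primary and key secondary endpoints and the 121 events are untouched. Severity is minor.

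**What to change.** Delete the Sign Test sentence from 13.1.5, and check that Amendment 1.1 and the SAP do not carry it. Keep the Wilcoxon rank-sum test with its Hodges-Lehmann estimate for all ten measures, whatever the skewness.

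As an optional improvement, add a rank ANCOVA that adjusts for baseline and for the randomization strata (UDCA use and bilirubin category), in line with 13.1.3, 13.1.4 and 13.1.6.1, and label the Hodges-Lehmann interval as the unadjusted shift. The cost is wording in the protocol or SAP; no new data are needed and the sample size does not change.
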